5 INTRODUCTION

5.1 Background

Pain is one of the most common symptoms for which patients seek medical attention. Current treatment options for pain are limited by poor efficacy and high rates of adverse events (AEs), leaving many patients without adequate pain control. Nonsteroidal anti-inflammatory drugs (NSAIDs) pose a potentially serious risk of gastrointestinal toxicity with acute and chronic use, hematologic toxicity with acute use, and nephrotoxicity with chronic use.¹ Opioids are significantly limited by safety and tolerability issues and have a high abuse liability. Opioid-associated deaths have increased in frequency over the past 2 decades.² Opioids were involved in more than 70,000 overdose deaths in the US in 2020 and in approximately 76% of fatal drug overdoses in the EU in 2019.^{3, 4}

Given the limited treatment options, combined with the risks and constrained utility of current treatments, the development of new analgesics with improved efficacy and safety profiles is vital for better pain management and patient health outcomes. Despite the need for new analgesics, clinical development has exhibited a considerable lack of recent progress and innovation of new medications to treat pain.⁵ Over the last decade, the majority of approved analgesic drugs either act on the opioid receptor system or are NSAIDs⁶; few new molecular entity drugs for moderate to severe pain have been approved.^{7, 8} The majority of research activity focuses on developing abuse-deterrent reformulations of existing narcotic pain drugs, or combinations with NSAIDs. The resultant compounds do not have substantially improved efficacy or safety.

Voltage-gated sodium channel 1.8 (Nav1.8) plays a critical role in pain signaling.^{9, 10} Support for this assertion arises from (1) evaluation of the role Nav1.8 plays in normal physiology¹¹⁻¹⁵, (2) pathological states arising from mutations in the Nav1.8 gene (SCN10A)^{16, 17}, (3) animal models¹⁸⁻²¹, and (4) pharmacology of known Nav1.8-modulating agents.²²⁻²⁴ In addition, because Nav1.8 expression is restricted to peripheral neurons, particularly those that sense pain (e.g., the dorsal root ganglia [DRG])^{11, 13}, Nav1.8 inhibitors are less likely to be associated with the side effects commonly observed with other sodium channel modulators and the abuse liability associated with opioid therapies. Therefore, targeting the underlying biology of pain through selective Nav1.8 inhibition represents a novel approach to analgesic drug development that has the potential to address an urgent unmet need for safe and effective acute and chronic pain therapies. These therapies include treatment where the primary mechanisms underlying pain are nociceptor hyperexcitability.

5.2 Study Rationale

This study will evaluate the safety and effectiveness of up to 14 days of treatment with VX-548 for acute pain.

6 STUDY OBJECTIVES

6.1 **Primary Objective**

To evaluate the safety and tolerability of VX-548

6.2 Secondary Objective

To evaluate the effectiveness of VX-548 in treating acute pain

7 STUDY ENDPOINTS

7.1 Primary Endpoint

Safety and tolerability based on treatment-emergent adverse events (TEAEs), laboratory test results, vital signs, and ECGs

7.2 Secondary Endpoint

Subject perception of VX-548 effectiveness in treating pain at the end of treatment as measured by the proportion of subjects reporting good, very good, or excellent on a patient global assessment (PGA)

8 STUDY POPULATION

Eligibility will be reviewed and documented by an appropriately qualified member of the investigator's team before subjects are enrolled.

Subjects who meet all of the inclusion criteria and none of the exclusion criteria will be eligible.

8.1 Inclusion Criteria

All Subjects (Before Surgery, If Applicable)

- 1. Subject will sign and date an informed consent form (ICF).
- 2. Willing and able to comply with scheduled visits, treatment plan, study restrictions, laboratory tests, contraceptive guidelines, and other study procedures.
- 3. Subjects (male and female) between the ages of 18 and 80 years, inclusive.
- 4. Body mass index (BMI) of ≥ 18.0 to < 40.0 kg/m².
- 5. **Surgical subjects:** Scheduled to undergo an ambulatory orthopedic, plastic, breast, otorhinolaryngologic, colorectal, gynecologic, urologic, or general surgical procedure with pain that is expected to last for at least 72 hours and that is expected to require no more than short-term (i.e., <24-hour) admission (additional details on ineligible procedures are provided in Appendix A).

Non-surgical subjects: Present to medical facility with pain of new origin (not related to a prior known condition) that is moderate or severe on the verbal categorical rating scale (VRS) and \geq 4 on the numeric pain rating scale (NPRS), has been ongoing for \leq 48 hours, is expected to last for at least 72 hours, and is expected to require no more than a short-term (i.e., <24-hour) admission, if any. Representative conditions include traumatic and atraumatic acute musculoskeletal pain, orofacial pain, burns, and cutaneous and soft tissue pain (additional details on ineligible conditions are provided in Appendix A).

After Surgery (Surgical Subjects Only)

- 6. Subject reported pain at the surgical site that is moderate or severe on the VRS and ≥4 on the NPRS within the following procedure-specific time periods:
 - Procedures performed with regional anesthesia: within 12 hours after surgery completion
 - All other procedures: within 4 hours after surgery completion

- 7. Subject is lucid, able to follow commands, and able to swallow oral medications.
- 8. All analgesic guidelines (Section 9.4.1) were followed during and after the procedure.

8.2 Exclusion Criteria

All Subjects (Before Surgery, If Applicable)

- 1. **Surgical subjects only:** History of previous surgery due to the same condition, except for procedures for which a previous surgery on the contra-lateral limb or organ is allowed.
- 2. **Surgical subjects only:** History of a prior surgical procedure in the same region of the body that resulted in any perioperative complications or that, in the opinion of the investigator or medical monitor, would preclude participation in the study.
- 3. History of any illness or any clinical condition that, in the opinion of the investigator, might confound the results of the study or pose an additional risk in administering study drug to the subject. This may include, but is not limited to, history of relevant drug or food allergies; history of significant respiratory, cardiovascular, metabolic, hematologic, neurologic, or psychiatric disease; history or presence of clinically significant pathology; and history of cancer. Note that this criterion does not apply to squamous cell skin cancer, basal cell skin cancer, and Stage 0 cervical carcinoma in situ (i.e., no adjudication by the investigator is needed), so long as there has been no recurrence for the last 5 years.
- 4. Cardiac dysrhythmias requiring anti-arrhythmic treatment(s) within the last 2 years; history or evidence of abnormal study ECGs that in the opinion of the investigator or medical monitor would preclude the subject's participation in the study; or history of QT prolongation or standard 12-lead ECG (performed in triplicate) demonstrating median QTcF >450 msec at screening.
- 5. Presence of an automated implantable cardioverter defibrillator, cardiac resynchronization therapy device, or pacemaker.
- 6. History of significant hepatic disease, including but not limited to hepatic cirrhosis, portal hypertension, or moderate or severe hepatic impairment (defined as Child Pugh Class B or C²⁵).
- 7. Alanine transaminase or aspartate transaminase values $>2.5 \times$ upper limit of normal.
- History of severe renal impairment defined as estimated glomerular filtration rate (eGFR)
 <30 mL/min/1.73² calculated using the subject's measured serum creatinine; the suggested calculation method for eGFR is the Chronic Kidney Disease Epidemiology Collaboration (CKD-EPI) equation
- 9. Any other abnormal laboratory results indicative of significant medical disease that, in the opinion of the investigator, would preclude the subject's participation in the study.
- 10. History of any sensory abnormality that, in the opinion of the investigator, may confound the ability of the subject to assess pain.
- 11. Subjects who have a painful physical condition that, in the opinion of the investigator, may confound the assessments of pain.

- 12. A known or clinically suspected active infection with human immunodeficiency virus or hepatitis B or C viruses. (**Note:** Testing in the absence of suspected active infection is required for surgical subjects only.)
- 13. Any surgery (except the protocol surgery for surgical subjects) within 1 month before the first study drug dose, unless approved by the medical monitor.
- 14. American Society of Anesthesiologists physical status classification²⁶ of \geq 3.
- 15. Chronic use of opioids (pure agonists, agonist/antagonists, partial agonists, antagonists) or NSAIDs with dose escalation within 30 days before first dose of study drug.
- 16. Unwilling or unable to stop analgesics at least 5 half-lives or 2 days (whichever is longer) before first dose of study drug, with the following exception: for non-surgical subjects, use of a limited amount of pain medications before presentation at the medical facility and/or single use of any medication in the medical facility within the past 4 hours is not exclusionary.
- 17. Subjects who have started any non-analgesic new medications that have not been at a stable dose for at least 14 days before first dose of study drug.
- 18. Subjects unwilling to receive any protocol-related medicine (e.g., ibuprofen, acetaminophen, fentanyl).
- 19. Subjects with a history of allergy or significant adverse event (AE) to any opioid and/or NSAID that, in the opinion of the investigator, would significantly increase the chance of AEs from medicines used in the study.
- 20. Subjects with sleep apnea and/or on a home positive airway pressure device.
- 21. History of peptic ulcer disease or gastrointestinal bleeding that, in the opinion of the investigator or medical monitor, would preclude the subject's participation in the study.
- 22. For female subjects: Pregnant, nursing, or planning to become pregnant during the study or within 30 days after the last study drug dose.

For male subjects: Male subjects with a female partner who is pregnant, nursing, or planning to become pregnant during the study or within 30 days after the last study drug dose.

- 23. Participation in a previous study investigating VX-548.
- 24. Participated in another investigational study within 30 days of the first dose of study drug.
- 25. Evidence of misuse, aberrant use, or addiction to alcohol or an illicitly used drug of abuse in the past 3 years, or a positive test for drugs of abuse as defined in Section 11.5.2.
 - A positive drug screen for a known prescribed concomitant medication that is not otherwise exclusionary (e.g., benzodiazepines) will not disqualify subjects.
- 26. Use of the substances, activities, or devices, as indicated in Section 9.4, during the specified times.
- 27. Subject, or close relative of the subject, is the investigator or a subinvestigator, research assistant, pharmacist, study coordinator, or other staff directly involved with the conduct of the study at that site.

After Surgery (Surgical Subjects Only)

- 28. Subject had any surgical complications during the procedure.
- 29. Subject had a medical complication during the procedure that, in the opinion of the investigator, should preclude assignment to treatment.
- 30. Standard 12-lead ECG (performed in triplicate) demonstrating median QTcF >450 msec at baseline (Day 1 predose).

9 STUDY IMPLEMENTATION

9.1 Study Design

This is a Phase 3, single-arm study evaluating the safety and effectiveness of VX-548 in treating acute pain (Figure 9-1 [surgical subjects] and Figure 9-2 [non-surgical subjects]).

Figure 9-1 VX22-548-107 Study Design (Surgical Subjects)

NPRS: numeric pain rating scale; VRS: verbal categorical rating scale

Notes: After surgery completion, a subject will be assigned to treatment if (1) the subject requests the first dose of study drug for pain relief, (2) the subject's pain is moderate or severe on the VRS, and (3) the subject's pain is ≥4 on the NPRS. If a subject does not meet the VRS and NPRS criteria within the protocol-specified, procedure-specific time period, the subject will not be eligible for this study. Figure is not drawn to scale.

Figure 9-2 VX22-548-107 Study Design (Non-surgical Subjects)

NPRS: numeric pain rating scale; VRS: verbal categorical rating scale

Notes: After completion of screening assessments and confirmation of eligibility, a subject will be assigned to treatment if (1) the subject's pain is moderate or severe on the VRS, and (2) the subject's pain is ≥4 on the NPRS. Figure is not drawn to scale.

Surgical Subjects

On Day 1, subjects will undergo a scheduled ambulatory surgical procedure with pain that is expected to last for at least 72 hours and that is expected to require no more than a short-term (i.e., <24-hour) admission. After surgery completion, a subject will be assigned to treatment if (1) the subject requests the first dose of study drug for pain relief, (2) the subject's pain is moderate or severe on the VRS, and (3) the subject's pain is \geq 4 on the NPRS. If a subject does not meet the VRS and NPRS criteria within the protocol-specified time period for the surgical procedure they underwent (e.g., 4 hours for most procedures; Section 8.1), the subject will not be eligible for this study.

Non-surgical Subjects

On Day 1, after completion of screening assessments and confirmation of eligibility, a subject will begin treatment if (1) the subject's pain is moderate or severe on the VRS, and (2) the subject's pain is \geq 4 on the NPRS. For a subject to be eligible, their pain must have been ongoing for \leq 48 hours at presentation.

All Subjects

Approximately 250 subjects will receive VX-548 (100 mg first dose, then 50 mg every 12 hours [q12h]). Subjects will continue to receive VX-548 for 14 days or until their pain resolves, whichever occurs first. An acetaminophen/ibuprofen combination may be used as a rescue medication for pain relief as needed (prn), starting any time after the first dose of study drug through Day 14, completion of study drug treatment due to pain resolution, or study drug discontinuation, whichever occurs first. Subjects will be permitted to take acetaminophen 650 mg/ibuprofen 400 mg every 6 hours (q6h) prn, up to a maximum of 2600 mg/1600 mg in any 24-hour period.

The following approach will be used to define pain resolution and completion of study drug treatment:

- 1. Pain is considered to be resolved and the study drug treatment will be considered completed if
 - a. a subject takes no study drug during a 48-hour period (i.e., skipped at least 4 consecutive doses due to pain resolution); and
 - b. a subject takes no more than 1 dose of acetaminophen/ibuprofen during each 24-hour period within the 48-hour period (i.e., no more than 2 doses in 48 hours).
- 2. If a subject stops taking study drug per Criterion 1a but does not meet Criterion 1b, they will be instructed to restart study drug (and prn rescue medication).
- 3. If a subject stops and restarts study drug (Criterion 2 above) and subsequently believes their pain is resolving and stops study drug a second time, they will be instructed to **not** restart study drug, regardless of whether the above criteria are met.
- 4. If a subject stops study drug a second time after the restart of dosing (Criterion 3 above) and then fulfills both Criterion 1a and 1b, the pain is considered resolved and study drug treatment will be considered completed. If the subject fulfills Criterion 1a but not Criterion 1b after the restart of dosing, the pain is considered not resolved and study drug will be considered discontinued.

Note If a subject stops study drug due to pain resolution less than 48 hours before the last scheduled dose of study drug (i.e., stops after the second dose on Day 12) and therefore cannot meet Criterion 1a by Day 14, the subject will be considered to have completed study drug dosing as long as they also meet Criterion 1b.

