Vital signs	Х	Performed after surgery completion (at least 1 hour after surgery completion is recommended) before the first dose of study drug. Vital signs will be collected after a ≥5-minute rest (seated or supine) and before any 12-lead ECG assessment or blood sampling; Section 11.5.3.				
Standard 12-lead ECG	Х	Performed after surgery completion (at least 1 hour after surgery completion is recommended) before the first dose of study drug. Standard 12-lead ECGs will be performed in triplicate after a \geq 5-minute rest (supine); these will be done after taking vital signs and before any procedures that may affect heart rate (e.g., blood sampling); Section 11.5.4.				
VRS	Х	Completed upon request for the first dose of study drug for pain relief after surgery completion; Section 9.1.2.				
NPRS	Х	Completed immediately after the VRS only if the subject's pain is rated moderate or severe on the VRS; Section 9.1.2.				
Medications review	Continuous from signing of ICF through completion of study participation	All medications taken within 14 days before the Screening Visit through completion of study participation; Section 9.4.2.				
Nonpharmacological treatment and procedures review	Continuous from signing of ICF through completion of study participation	All nonpharmacological treatments and procedures starting from the Screening Visit.				
Adverse events	Continuous from signing of ICF through completion of study participation	Section 11.5.1				

Table 3-2Study VX22-548-107: Procedure Through Treatment Assignment
(Surgical Subjects)

ICF: informed consent form; NPRS: numeric pain rating scale; VRS: verbal categorical rating scale

^a Subject must complete all Day 1 predose assessments before the first dose of study drug is administered. When assessment time points coincide, assessments will be performed in the following order: vital signs, 12-lead ECG, and blood sample collection.

	Saraaning Visit/Day 1				
	Screening Visit/Day 1	-			
Event/Assessment ^a	Screening Through Treatment Assignment	Comments			
Presents with pain at medical	X	Section 9.1			
facility (e.g., hospital, clinic, or ambulatory center)					
Informed consent	Х	Must be obtained before performing any study-related procedures; Section 13.2.3.			
Demographics	Х	Section 11.1			
Medical and surgical history	Х	Section 11.1			
History of drug and alcohol use	Х	Section 8.2			

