PGA		X			X	X	X		Recorded in the e-diary ^d ; Section 11.4.1. Subjects should still complete the PGA even if the specified dose is not taken. Day 2: To be completed after the third study drug dose (approximately 24 hours after the first dose). Day 7: Completed after the first study drug dose on Study Day 7 (whether or not this coincides with the date of the Day 7 Visit). Day 14 or EDV: Completed after final study drug dose for subjects still taking study drug on Day 14. Subjects who have discontinued or completed study drug treatment should complete the PGA at home within approximately 24 hours after the last (or presumed last) dose of study drug rather than waiting for their scheduled visit.
Vital signs			X (postdose) ^b		Х	х	Х	Х	Vital signs will be collected after a \geq 5-minute rest (seated or supine) and before any 12-lead ECG assessment or blood sampling; Section 11.5.3.
Standard 12-lead ECG	at discharg	ours after first e or before lea ility, as applic	ving medical		X (4 hours after a dose) ^e	X (4 hours after a dose) ^{e,f}	X	(X)	Required at SFU only if any clinically significant abnormalities were noted on a prior ECG. Standard 12-lead ECGs will be performed in triplicate after a ≥5-minute rest (supine); these will be done after taking vital signs and before any procedures that may affect heart rate (e.g., blood sampling); Section 11.5.4.

Table 3-4Study VX22-548-107: Treatment Period and Safety Follow-up Visit (All Subjects)

Table 3-4Study VX22-548-107: Treatment Period and Safety Follow-up Visit (All Subjects)

Event/Assessment ^a	Day 1	Day 2	Discharge ^b	Day 4 (± 1 day)	Day 7 (± 1 day)	Day 14 (+ 3 days)	End of Dosing Visit ^c	Safety Follow-up Visit Day 28 (± 2 days)	Comments
Symptom-directed PE				As applicable					Symptom-directed PEs will occur at any time during the study if triggered by AEs or if deemed necessary by the investigator; Section 11.5.3.
Focused PE (surgical subjects only)								Х	Assessment of wound healing at the operative site; Section 11.5.3.
Complete PE								(X)	Required at SFU only if a clinical finding during the Treatment Period requires follow up, in which case the subject must have a clinic visit; Section 11.5.3.
C-SSRS			X (postdose) ^b		Х	Х	X		Section 11.5.5
Urine β-hCG						Х	Х	Х	All female subjects of childbearing potential; Section 11.5.2.
Serum chemistry			X (postdose) ^b			Х	X	(X)	Required at SFU only if a clinical finding during the Treatment

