9.4 Study Restrictions

Study restrictions that apply to all subjects are summarized in Table 9-1. Additional details on study restrictions will be provided in the Study Reference Manual.

Restricted	Timing of Restriction				
Medication/Food/Activity ^a	Start	Stop			
Other investigational drugs or devices	30 days before first dose of study drug, 5 half-lives before first dose of study drug, or time determined by local requirements (whichever is longest)	Completion of SFU assessments			
Analgesic medications	Surgical subjects: 5 half-lives or 2 days (whichever is longer) before admission for surgery and per guidelines in Section 9.4.1.1 and Section 9.4.1.2 Non-surgical subjects: at presentation with acute non-surgical pain (see also Section 8.2 and Section 9.4.1.2)	Until last dose of study drug is taken			
Oral steroids	5 half-lives or 2 days (whichever is longer) before admission for surgery or at presentation with non-surgical pain	Until last dose of study drug is taken			
Medications, herbal and dietary supplements (including St. John's wort) known to be moderate or strong inducers of CYP3A	14 days before first dose of study drug	Completion of SFU assessments			
Medications, herbal and dietary supplements known to be moderate or strong inhibitors of CYP3A	7 days before first dose of study drug	Completion of SFU assessments			
Grapefruit or grapefruit juice; pomelos, star fruit, and Seville oranges or their juices	7 days before first dose of study drug	Completion of SFU assessments			
H2 blockers and proton pump inhibitors	72 hours before first dose of study drug	Until last dose of study drug is taken			
Alcohol	24 hours before first dose of study drug	Until last dose of study drug is taken			
Strenuous exercise (e.g., heavy lifting, weight training, and aerobics)	48 hours before first clinical laboratory testing	Completion of SFU assessments			

Table 9-1Study Restrictions

H2: histamine type 2 receptor; SFU: Safety Follow-up

^a Refer to the Study Reference Manual for a more complete list of medications prohibited/restricted in the study. See Section 9.4.2 for guidance on concomitant medications.

Surgical Subjects Only

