9.4.1.2 Rescue Medication

Rescue medication may be used per the following guidelines:

- Rescue medication for pain relief may be used prn any time after the first dose of study drug through Day 14, completion of study drug treatment due to pain resolution, or study drug discontinuation (e.g., due to AE), whichever occurs first. Subjects will continue to document rescue medication use through Study Day 14 or the EDV, whichever occurs first.
- Subjects will be permitted to take acetaminophen 650 mg/ibuprofen 400 mg q6h prn, up to a maximum of 2600 mg/1600 mg in any 24-hour period.
- No other analgesic medications (e.g., NSAIDs other than ibuprofen, opioids) are allowed from the start of the treatment period through the last dose of study drug.
- A record (date and time of administration) will be kept of all rescue medication use.

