7 OVERALL DESIGN

This is a Phase 3, single-arm study evaluating the safety and effectiveness of VX-548 in treating acute pain (Figure 7-1 [surgical subjects] and Figure 7-2 [non-surgical subjects]).

Surgical Subjects

On Day 1, subjects will undergo a scheduled ambulatory surgical procedure with pain that is expected to last for at least 72 hours and that is expected to require no more than a short-term (i.e., <24-hour) admission. After surgery completion, a subject will be assigned to treatment if (1) the subject requests the first dose of study drug for pain relief, (2) the subject's pain is moderate or severe on the VRS (verbal categorical rating scale), and (3) the subject's pain is

 \geq 4 on the NPRS (numeric pain rating scale). If a subject does not meet the VRS and NPRS criteria within the protocol-specified time period for the surgical procedure they underwent (e.g., 4 hours for most procedures), the subject will not be eligible for this study.

Non-surgical Subjects

On Day 1, after completion of screening assessments and confirmation of eligibility, a subject will begin treatment if (1) the subject's pain is moderate or severe on the VRS, and (2) the subject's pain is \geq 4 on the NPRS. For a subject to be eligible, their pain must have been ongoing for \leq 48 hours at presentation.

All Subjects

Approximately 250 subjects will receive VX-548 (100 mg first dose, then 50 mg every 12 hours [q12h]). Subjects will continue to receive VX-548 for 14 days or until their pain resolves, whichever occurs first. An acetaminophen/ibuprofen combination may be used as a rescue medication for pain relief as needed (prn), starting any time after the first dose of study drug through Day 14, completion of study drug treatment due to pain resolution, or study drug discontinuation, whichever occurs first. Subjects will be permitted to take acetaminophen 650 mg/ibuprofen 400 mg every 6 hours (q6h) prn, up to a maximum of 2600 mg/1600 mg in any 24-hour period.

The following approach will be used to define pain resolution and completion of study drug treatment:

- 1. Pain is considered to be resolved and the study drug treatment will be considered completed if
 - a. a subject takes no study drug during a 48-hour period (i.e., skipped at least 4 consecutive doses due to pain resolution); and
 - b. a subject takes no more than 1 dose of acetaminophen/ibuprofen during each 24-hour period within the 48-hour period (i.e., no more than 2 doses in 48 hours).

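### Criterion 1b tests claimed pain resolution by counting acetaminophen/ibuprofen only, so use of another analgesic for the same pain does not count against a 'resolved/completed' label

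*Protocol*

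**What the plan says.** Protocol 9.1 sets two conditions for pain resolution and treatment completion. Criterion 1a asks for 48 hours without study drug, glossed as "skipped at least 4 consecutive doses due to pain resolution". Criterion 1b asks for "no more than 1 dose of acetaminophen/ibuprofen during each 24-hour period within the 48-hour period (i.e., no more than 2 doses in 48 hours". The Synopsis has the same rule, and so does SAP Section 7, down to the gloss "i.e., no more than 2 doses in 48 hours". None of the three places mentions another analgesic.

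A subject who meets 1a but not 1b is told to restart (Criterion 2). After a second stop, failing 1b means not resolved and discontinued (Criterion 4). Under the Note to 9.1, a subject who stops too late to complete 48 hours by Day 14 is still a completer if 1b is met.

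The ban on other analgesics has a different end point. Section 9.4.1.2 says "No other analgesic medications (e.g., NSAIDs other than ibuprofen, opioids) are allowed from the start of the treatment period through the last dose" (meaning the last VX-548 dose), and Table 9-1 ends the analgesic restriction with "Until last dose of study drug is taken". Study rescue remains available until Day 14, "completion of study drug treatment due to pain resolution, or study drug discontinuation (e.g., due to AE), whichever occurs first".

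Protocol 9.5 records all medications to the end of participation, with indication and start and stop dates. SAP 9.2.4 summarizes concomitant medications by Preferred Name and lists them.

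**The concern.** Criterion 1b treats analgesic use as evidence against a claim that pain has resolved, but it sees only one product. Once a subject meets 1a and 1b there is no restart, so the dose before the 48 hours stands as the last dose. An opioid or a different NSAID taken in those 48 hours is then neither prohibited nor counted.

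Nothing else in the schedule tests the stated reason objectively:

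- The VRS is "Completed upon request for the first dose of study drug for pain relief after surgery completion" (Table 3-2). The NPRS follows it, and Table 3-3 places both before treatment assignment for non-surgical subjects. Table 3-4 contains neither.
- The PGA rates the study drug, not current pain. For early stoppers it is due "within approximately 24 hours after the last (or presumed last) dose of study drug", before the 48 hours are over.

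At stake are who is told to restart, the disposition category and reason (SAP 9.2.1), and the completed/discontinued split of exposure (SAP 9.2.5). No planned table links other-analgesic use to disposition or to the 48 hours.

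**Working it through.** The plan gives no figure for this point, and its sample-size probabilities do not enter it. The check applies the rule to example dosing patterns.

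**Inputs.** Let a1 and a2 be the acetaminophen/ibuprofen doses in the first and second 24 hours off study drug, and o1 and o2 the doses of any other analgesic for the index pain (the pain for which study drug was given). Assume that the site accepts the stated reason, so 1a is met.

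- 1b as written (Protocol 9.1): met if a1 ≤ 1 and a2 ≤ 1.
- 1b counting any analgesic: met if a1 + o1 ≤ 1 and a2 + o2 ≤ 1.
- Zero tolerance for other analgesics, for comparison: as written, and o1 + o2 = 0.

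| (a1, a2) | (o1, o2) | As written | Any analgesic counted | Zero tolerance |
|---|---|---|---|---|
| (0, 0) | (0, 0) | met | met | met |
| (1, 1) | (0, 0) | met | met | met |
| (2, 0) | (0, 0) | not met | not met | not met |
| (0, 0) | (4, 4) | met | not met | not met |
| (1, 1) | (4, 4) | met | not met | not met |
| (0, 0) | (1, 0) | met | met | not met |

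The (4, 4) rows are another analgesic every 6 hours: 48/6 = 8 doses. The third row fails on the per-24-hour limit, although its total of 2 agrees with the parenthesis in 1b. A pattern of (3, 0) fails on either reading, so the contrast does not depend on this.

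**Position of the ban.** If the subject restarts, the 48 hours precede the eventual last dose and fall inside the ban. If 1a and 1b are met there is no restart, and the 48 hours follow the last dose and fall outside it. The gap therefore exists where the 'resolved' label is given.

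**Size.** Disposition percentages are based on the FAS, about 250 subjects: 1/250 = 0.4 percentage points per relabelled subject. The documents give no rate. If 1% to 10% of subjects were labelled this way (an assumption for scale only), that would be 250 × 0.01 = 2.5 to 250 × 0.10 = 25 subjects.

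**What dates alone can show.** Let the last dose be at clock hour h on date D. The 48 hours run from h on D to h on D+2. Dates D through D+2 span 72 hours, of which h hours precede the dose and 24 − h follow the end of the period. So 24 hours lie outside and 72 − 24 = 48 inside, whatever h is (h = 20: 20 before, 4 after). Only D+1 lies wholly inside for every h. A count from dates is therefore a range: certain if D+1 is covered, possible if any of D to D+2 is.

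**The case against.** The strongest reply is that resolution needs 1a as well as 1b. A subject taking an opioid every 6 hours for the same pain has hardly skipped doses because the pain resolved, and the investigator may refuse the label. The setting also makes the case uncommon:

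- Supplied rescue stays available during the 48 hours, and 1b counts it.
- Subjects are instructed on the restrictions, and at a first stop they cannot be sure that the dose was their last.
- The End of Dosing Visit is a clinic visit, ideally within 72 hours of the last dose (Protocol 9.1.5), and medications are asked about at every visit or telephone contact (9.5).
- The analyses are descriptive, and the planned disposition and medication listings can be joined.

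Most of this stands and keeps the point small. It does not close the gap. The reason in 1a is the subject's own account, and the rule does not tell the site to weigh other analgesics against it. For late stoppers under the Note, 1b is the only remaining check on that account. Joining listings is possible but not planned. The Study Reference Manual and the protocol deviation plan are not among the documents and might add a rule.

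A reader might infer that the other analgesic goes unseen. It does not: Protocol 9.5 and SAP 9.2.4 have it recorded with its indication and listed. A reader might also infer that the ban should run past the last dose. That would be a mistake, because study rescue ends at discontinuation, and subjects who discontinue while still in pain would have no permitted analgesic.

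**Conclusion.** The gap in the rule is real and its consequence is minor. Conditional on the site accepting the stated reason, a subject using another analgesic for the index pain can be labelled resolved and completed and not be told to restart, while lighter use of the study's own rescue product can fail.

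The documents do not support reading this as a bias in the study's endpoints. The Safety Set and the FAS need only one dose of study drug. The end-of-treatment PGA is defined for completers and discontinuers alike (SAP 9.3), so relabelling a subject changes neither the responder definition nor the denominator.

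The size is 0.4 points of the completed percentage per subject, with unknown frequency. That figure gives the scale of relabelling, not of harm. The conclusion rests on the wording of the protocol and SAP and on no supplementary manual adding a condition. This is a cheap improvement of low severity.

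**What to change.** **Preferred.** In the Synopsis, Protocol 9.1 and SAP Section 7, make 1b count any analgesic taken for the index pain, whether the acetaminophen/ibuprofen combination or another, against the existing limit of one dose per 24 hours. A zero-tolerance clause would be worse: one tablet of another NSAID would fail while two combination doses, one per day, would pass. Leave Criteria 2 to 4, Table 9-1 and Section 9.4.1.2 unchanged, and add no new rule for subjects who do not restart.

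**If the protocol is closed.** Add one descriptive row to the SAP 9.2.1 disposition table: subjects completed for pain resolution who had a non-rescue analgesic for the index pain. Show it as certain (dates cover the day after the last dose) and possible (dates cover any day from the last-dose date through 2 days later), using recorded times where available. Because 9.5 asks for start and stop dates rather than each dose, the row counts use, not failures of the reworded 1b.

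**Cost.** One phrase in three places, or one table row from data already collected. Sites must ask about the timing and number of out-of-clinic doses. A few subjects may be told to restart or move from completed to discontinued.
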